Since so many biologic functions depend upon correct protein and lipid glycosylation, clinical CDG manifestations are widely variable within and among subtypes and across the lifespan. The clinical findings in affected individuals reflect glycosylation's role in the embryology and biology of many organ systems. Clinical findings may include developmental delay/intellectual disability with abnormalities in brain MRI, hypotonia, failure to thrive or growth impairment, hepatopathy, coagulopathy, immunodeficiency, protein losing enteropathy, osteopenia, skeletal dysplasias, renal abnormalities, functional and/or anatomic eye involvement, endocrinopathies, and peripheral neuropathy. Some CDG present with only tissue-specific symptoms such as SEC23B-dyserythropoietic anemia or Leukocyte Adhesion Deficiency Type II.⁶

Of the known 137 glycan-synthesis disorders we have potential therapies for only 8 disorders and not all current therapies are fully effective. Clinical trials have not validated these treatments for safety and efficacy. MPI-CDG has been treated with oral mannose.⁷ In SLC35C1-CDG, some patients respond to oral fucose supplementation. This treatment is only effective for the typical recurrent infections with hyperleukocytosis and does not correct the neurological issues of these patients.⁶ PIGM-CDG, the mutation described in the only published case so far, causes histone hypoacetylation at the PIGM promoter. Butyrate controls the seizures.⁸ PGM1, a critical enzyme for the

conversion of glucose-1-phosphate to glucose-6-phosphate, is at the crossroads of the glycogen, glucose and galactose pathway. **PGM1 deficiency is treatable with D-galactose**, alleviating the hypoglycemia, coagulopathy, and endocrinopathy seen in this disorder,^{9,10} although not the cardiomyopathy. The glycosylation defect CAD-CDG has been treated with uridine.^{11,12} Magnesium can improve MAGT1-CDG. Manganese and D-galactose have been used to treat TMEM165-CDG, whereas **SLC35A2-CDG has been treated with D-galactose**. From the group of disorders of de-glycosylation preclinical trials suggested positive effect of **GlcNAc treatment in NGLY1** deficiency.

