A list of retrospective data to be collected from the medical record is attached to the application. Optional blood, stool, and urine samples will be collected for research at each annual visit (once per year over the course of 5 years of follow up). If a participant is unable to provide urine, stool, or blood samples due to age or other logistical difficulty, we will forego research sample collection and rely purely on clinical/research data collected over the course of the study. If any clinical residual samples (urine, blood, or stool) are available for these participants unable to provide fresh research collections, we may use these instead. These clinical residuals would come from the Biochemical Genetics Lab (BGL) at Mayo or from participating sites' laboratories, if any sample remains. Skin biopsies will be only taken for diagnostic purposes. Leftover tissue material from clinical diagnostics will be used for biomarker discovery. If a subject doesn't complete regular follow up appointments, we will reach out to them via phone or email to obtain follow up information and complete questionnaires to ensure we are able to obtain accurate follow up information. Participants will be offered up to \$700 reimbursement to cover lodging and travel expenses, per visit at all sites except for the University of Minnesota Masonic Children's Hospital. University of Minnesota will offer \$75 per visit to each participant as remuneration and will not offer travel reimbursement.

Accrual:

Our goal is to enroll 150 patients of all ages and from all CDG types over 5 years in the natural history study. At least 50 of the 150 enrolled subjects will have a diagnosis of PMM2-CDG. There will be no exclusion based on sex, ethnicity or socio-economic status. The sample size of 100 was based on a count of the number of affected individuals currently clinically followed and current patient census taken by CDG CARE in August of 2018.

Participating Sites:

We will collaborate with other sites on this study with Mayo Clinic acting as the IRB of record. The target accrual in total will remain at 150 participants. The sites below will be included in the study:

1. Children's Hospital of Pittsburgh at University of Pittsburgh Medical Center – PI is [name]
2. Seattle Children's Hospital – PI is [name]
3. Tulane University Medical School – PI is [name]
4. Baylor College of Medicine – PI is [name]
5. University of Minnesota Masonic Children's Hospital – PI is [name]

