Examples

- The study plans to conduct a retrospective chart review and ask subjects to complete a questionnaire.
- The study plans to include subjects previously diagnosed with a specific disease and add newly diagnosed subjects in the future.

The study will use data that have been collected under another IRB protocol. Include in the Methods section and enter the IRB number from which the research material will be obtained. *When appropriate, note when subjects have provided consent for future use of their data and/or specimens as described in this protocol.*

Enter one IRB number per line, add more lines as needed

Data Specimens Data & Specimens _____

Data Specimens Data & Specimens _____

Data Specimens Data & Specimens _____

Data Analysis

Data Analysis Plan: The study will be used to estimate the prevalence and distribution of scores and the precision of these estimates based on the specified sample size was assessed. For a binary variable (e.g. likelihood of moderate or severe for a given component of the severity score) the expected size of the confidence interval is a function of the sample size and true underlying prevalence.

The extensive clinical and laboratory data collected in this study will be recorded on electronic forms at each site and submitted to DMCC. Almost all of the clinical exams and laboratory studies will provide either a numerical score or categorical score for phenotypic severity, thereby allowing statistical analysis looking for longitudinal changes and exploring potential biomarkers that correlate with disease. We will utilize the statistical expertise of the DMCC for data analysis. The DMCC database will also be able to house imaging studies and genomic data collected from medical records in a de-identified way.

Clinical and laboratory measures, as well as demographics and age of onset, will be summarized using descriptive statistics. Principal component analysis (PCA) will be applied to summarize multivariate measurements. Baseline association between two factors of interest will be assessed using a general linear regression for a continuous response variable and logistic regression for a categorized response variable, after adjusting for potential confounders.

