With the data collected over time, the average trend with age will be estimated using mixed effects models to account for the correlation of repeated measures from a subject. The model will include fixed and random effects for the intercept and slope (age). Maximum likelihood estimates (MLE) will be obtained for regression coefficients for fixed effects and restricted MLE for the variance component. The association of a factor of interest with a response variable will be examined using mixed effects models to account for the subject specific change. For a time constant factor, the model will include the factor, age and an interaction term between the factor and age as fixed effects. The model will also include random effects for the intercept and slope (time). For a time varying factor, the model may include baseline value of the factor and the change at the next visit as fixed effects to estimate cross-sectional and longitudinal effects simultaneously.

We will compare results of PROs to NPCRS subdomain scores, physical exam findings, and laboratory findings that should be reflected in that tool to assess the validity of each PRO measure. Partial least squares (PLS) regression analysis will be utilized to identify patterns of association between the PROs and the clinical scores. The PLS analysis and significant weights may reveal novel composite scores for CDG patients. Changes in PRO scores over time will be tested for association with Quality of Life questions using random effects generalized linear regression models incorporating a random intercept for each participant. We will also compare subsequent scores on the PROs from the same subject to determine reliability of the PRO if there has been no significant interval change in the clinical status. Reliability will be assessed by the weighted Kappa to account for the ordinal variables.

Expected Outcomes.

References:

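### The longitudinal factor models do not carry forward the baseline confounder adjustment, so where a factor tracks CDG type and course differs by type, the factor-by-age term partly reflects type

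*Combined protocol and SAP*

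**What the plan says.** All the relevant text is in the combined protocol and SAP.

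- **Data Analysis Plan, baseline associations.** Linear regression is used for continuous responses and "logistic regression for a categorized response variable, after adjusting for potential confounders". No confounder is named.
- **Data Analysis Plan, longitudinal associations.** "For a time constant factor, the model will include the factor, age and an interaction term between the factor and age as fixed effects". A subject-level random intercept and slope are added. The slope is labelled as age in the preceding trend model and as time in this one.
- **Data Analysis Plan, changing factors.** "For a time varying factor, the model may include baseline value of the factor and the change at the next visit as fixed effects". No confounder is named here either.
- **Accrual.** "Our goal is to enroll 150 patients of all ages and from all CDG types over 5 years in the natural history study", and "At least 50 of the 150 enrolled subjects will have a diagnosis of PMM2-CDG".
- **Background.** "clinical CDG manifestations are widely variable within and among subtypes and across the lifespan". It also says that PMM2-CDG and galactosylation defects usually show an abnormal N-glycan pattern in blood, and that some CDG affect single tissues only.

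No longitudinal analysis stratified by CDG type is described.

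**The concern.** The factor-by-age coefficient is the plan's measure of whether a factor predicts the course of disease. The cohort mixes many genetic disorders, with a floor of one third for PMM2-CDG. Candidate factors such as a baseline biomarker pattern, age of onset or organ involvement may well be distributed differently across those disorders. With no type-by-age term, a difference in course between disorders can be credited to the factor, or can offset a real effect of the factor within disorders.

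The random intercept and slope do not protect against this. They describe correlation within a patient and are assumed independent of the factor. A main effect of type alone would not be enough either, because the bias is in the slope.

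At stake is whether a feature that only marks CDG type is reported as predicting progression, or a useful predictor is missed. Adjusted cross-sectional and unadjusted longitudinal results for the same factor would also not be comparable.

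**Working it through.** The plan states no figure to reproduce: it gives no SD, slope, effect size or alpha for these models.

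**Inputs from the documents.** There are 150 patients, at least 50 of them with PMM2-CDG (share 50/150 = 1/3). Visits are annual, and samples are taken "once per year over the course of 5 years of follow up", read here as 5 visits.

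**Inputs assumed.** Entry age 0 to 30, intercept SD 5, slope SD 0.5 per year, residual SD 2, a two-sided 5% test, and the factor prevalences and slope differences shown below.

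**Step 1: bias formula.** With type-by-age omitted,

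bias in factor-by-age = [P(PMM2 | F=1) − P(PMM2 | F=0)] × (PMM2 slope − slope in other types).

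- Factor in 60% of PMM2-CDG and 20% of others: P(F=1) = (1/3)(0.6) + (2/3)(0.2) = 0.333. Then P(PMM2 | F=1) = 0.2/0.333 = 0.6 and P(PMM2 | F=0) = 0.133/0.667 = 0.2. The difference is 0.4, so slope differences of 0.1, 0.2 and 0.3 give biases of 0.04, 0.08 and 0.12 per year.
- Factor in 80% and 10%: the difference is 0.8 − 0.1 = 0.7, giving 0.14 and 0.21 per year at slope differences of 0.2 and 0.3.
- Equal prevalence, or equal slopes: the bias is 0.

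**Step 2: false positives.** Simulation with no factor effect within type, two types, random slope on time, 3000 replicates, fitted by generalised least squares with the true covariance:

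| Prevalence (PMM2 / other) | Slope difference | Model as listed | With type and type-by-age |
|---|---|---|---|
| 60% / 20% | 0 | 5% | 5% |
| 60% / 20% | 0.1 | 8% | 5% |
| 60% / 20% | 0.2 | 16% | 5% |
| 60% / 20% | 0.3 | 31% | 5% |
| 80% / 10% | 0.2 | 39% | 5% |
| 80% / 10% | 0.3 | 70% | 5% |

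With the random slope on age instead (centred at 15), the 16% becomes about 10% and the 31% about 19%. The bias is the same, but the standard error is larger.

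**Step 3: masking.** The true factor effect is 0.2 per year, with the factor in 20% of PMM2-CDG and 60% of others. The difference in P(PMM2) is 0.143 − 0.5 = −0.357. At a slope difference of 0.3 the expected estimate is 0.2 − 0.357 × 0.3 = 0.093. Power for slope differences of 0.1, 0.2 and 0.3 is 56%, 37% and 22% as listed, against 65% adjusted.

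**Step 4: second set of assumptions.** REML fit, random slope on age, intercept SD 4, slope SD 0.5, residual SD 2, entry ages spread over 16 years, 200 replicates. With prevalence 70%/30%, a slope difference of 0.5 and no factor effect, the listed model gives a mean estimate of 0.175 (formula 0.181) and rejects in 30%. With 50%/50% prevalence it rejects in 5.5%, and with equal slopes in 5%. Adjusted rejection is 5% to 7% throughout (Monte Carlo error about 1.5 points). In these conditions a slope difference of 0.5, not 0.3, was needed to reach about 30%.

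**Step 5: cost of adjusting** (first set of assumptions, random slope on time).

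- Factor unrelated to type, effect 0.2: power 65% either way.
- Factor related to type, slopes equal, effect 0.2: power falls from about 65–68% to 58% (60%/20%) or 40% (80%/10%).
- Groups of 50 PMM2-CDG, 20 galactosylation and 80 other, with the factor excess and a 0.3 slope difference confined to 40 patients inside the last group: with three-group adjustment, rejection is still 16% (60%/20%) or about 38–41% (80%/10%), against 28% and 61% unadjusted.

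**The case against.** The best reply is that the text does not rule adjustment out. The plan lists what the model will include and does not say that nothing else may enter, and it relies on the coordinating centre's statistical expertise. A reader might infer that the plan restricts the model to these three terms, or that it adjusts for CDG type at baseline and then deliberately drops it. Neither is supported: the baseline sentence names no confounder, and CDG type is an inference from the Background and the accrual floor. What remains is that adjustment is written for one set of models and not for the next, so an analyst following the listed terms would fit an unadjusted model.

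Three further points stand and narrow the case.

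- Aim 1 concerns severity across CDG types, so type may itself be the factor. The listed terms then suit that purpose, and adding type again would make no sense.
- The work is partly exploratory. If the question is whether a marker tracks course across all CDG, the unadjusted slope is a legitimate descriptive quantity. Calling a result falsely significant presumes interest in the effect within type.
- The return to 5% in Step 2 holds by construction, because the simulated patients had exactly two types. Step 5 shows that grouping cures only part of the problem when the remaining group is itself mixed.

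**Conclusion.** The point holds conditionally. As listed, the longitudinal factor models leave out the confounder adjustment stated for baseline, and the factor-by-age term is confounded by CDG type when two things are both true: the factor is associated with type, and course differs by type. The Background makes both plausible but quantifies neither. If either fails, the bias is zero, so it would be wrong to conclude that every longitudinal association in this study will be biased.

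All sizes depend on assumed inputs. The central case (60%/20% prevalence, 0.3 per year) gives about 31% false positives with a random slope on time or about 19% with one on age, against 5% adjusted. Weaker association or smaller slope differences bring this close to nominal, and stronger ones raise it to 70%. The point does not reach the PRO-validity comparisons or the prevalence estimates. It is a worthwhile, inexpensive improvement to the plan and does not make the study unsound.

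**What to change.** In the Data Analysis Plan, after the two longitudinal factor models, add wording such as:

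> Unless CDG type is the factor being studied, the longitudinal models for both time-constant and time-varying factors will also contain grouped CDG type (PMM2-CDG; galactosylation defects; other), its interaction with age, and the confounders adjusted for in the matching baseline model. Patients whose diagnosis is pending will be assigned to a group once it is confirmed. The estimate without these terms will be shown alongside as descriptive. Where the factor and CDG type nearly coincide, an analysis within PMM2-CDG will be added.

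The baseline confounders should be named, since the plan does not list them.

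**Cost.** Wording only, because diagnosis is already recorded. Three groups add four fixed-effect parameters (two main effects, two interactions), plus whatever baseline confounders are chosen.

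**Downsides to state in the plan.** Power is lost when factor and type are related but slopes do not differ by type, and confounding can remain within the mixed residual group (Step 5). Results for factors concentrated in that group should be read with this in mind.

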IRB Minimal Risk Protocol Template

Note: If this study establishes a human specimen repository (biobank) for research purposes, do not use this template. Use the Mayo Clinic Human Specimen Repository Protocol Template found on the IRB home page under Forms and Procedures at <http://intranet.mayo.edu/charlie/irb/>

First-time Use: Use this template to describe your study for a new IRB submission.

1. Complete the questions that apply to your study.
2. Save an electronic copy of this protocol for future revisions.
3. When completing your IRBe application, you will be asked to upload this document to the protocol section.

Modification: To modify this document after your study has been approved:

1. Open your study in IRBe. Click on the study 'Documents' tab and select the most recent version of the protocol. Save it to your files.
2. Open the saved document and activate "Track Changes".
3. Revise the protocol template to reflect the modification points, save the template to your files
4. Create an IRBe Modification for the study and upload the revised protocol template.

General Study Information

Study Title: Clinical and Basic Investigations into Congenital Disorders of Glycosylation

Principal Investigator: [name]., Ph.D.

Protocol version number and date: Version 6 9/29/2020

Research Question and Aims

Objective: Define natural history, validate patient reported outcome and share knowledge on congenital disorders of glycosylation (CDG).

Aims:

Aim 1: Establish the prevalence and severity of specific morbid indicators of disease severity such as specific organ system involvement, degree of cognitive disability, and case-fatality associated with various CDG, and establish a dynamic platform to effectively disperse clinically relevant findings to families, non-expert clinicians and researchers, as well as provide a verified method to link these individuals to experts in CDG.

Aim 2: To validate the CDG rating scale and patient reported outcome /quality of life measures for CDG.

Background (*Include relevant experience, gaps in current knowledge, preliminary data, etc.*):

This clinical research study will determine the natural history of congenital disorders of glycosylation (CDG), delineate the spectrum of clinical features, develop and validate patient reported outcomes and disperse verified

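### The stated validity comparison for each PRO includes no non-matching domain, so by itself it cannot separate domain content from overall severity

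*Combined protocol and SAP*

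**What the plan says.** Research Question and Aims, Aim 2, reads: "To validate the CDG rating scale and patient reported outcome /quality of life measures for CDG". The method is in the last paragraph of the Data Analysis Plan. Each PRO is set against NPCRS subdomains, examination findings and "laboratory findings that should be reflected in that tool to assess the validity of each PRO measure". So the comparators are the ones expected to agree with the instrument.

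Three further PRO analyses follow:

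- "Partial least squares (PLS) regression analysis will be utilized to identify patterns of association between the PROs and the clinical scores". Significant weights from this step may suggest new composite scores.
- "Changes in PRO scores over time will be tested for association with Quality of Life questions", using models with a random intercept per participant.
- Repeat PRO scores in patients whose clinical status has not changed: "Reliability will be assessed by the weighted Kappa to account for the ordinal variables".

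Earlier in the same plan, baseline associations between two factors use linear regression for a continuous response and "logistic regression for a categorized response variable, after adjusting for potential confounders". The confounders are not named.

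On the population, Accrual says: "Our goal is to enroll 150 patients of all ages and from all CDG types over 5 years in the natural history study". Of these, 50 or more are to have PMM2-CDG. There are no exclusion criteria, and the Background says that "clinical CDG manifestations are widely variable within and among subtypes and across the lifespan".

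The documents give no non-matching comparator, no expected pattern of stronger and weaker correlations, no minimum correlation, no adjustment for overall severity, and no statement of what result would count against a PRO.

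**The concern.** A claim that a PRO measures a particular domain needs two kinds of evidence. It should agree with other measures of that domain, and it should agree with them more than with measures of other domains. The stated validity comparison supplies the first kind only.

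This matters more in a mixed cohort. Patients who are more severely affected overall may score worse on many scales at once. Two scales can then correlate because both follow overall severity, even if they share nothing about the named domain. A larger sample or a stricter cut-off on the matched correlation does not remove this ambiguity, because the quantity examined mixes the two sources.

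The Background says that CDG lacks a clear outcome measure for clinical trials, and Aim 2 is part of the answer. If a PRO is reported as a valid measure of one domain when it follows overall severity, a later user would read its scores wrongly.

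**Working it through.** The plan gives no power, alpha, expected correlation or threshold for PRO validation, so there is no figure to reproduce. The check asks how often a PRO with no domain-specific content would still show a significant correlation with its matching finding.

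**Inputs from the documents.** n=150 (Accrual) and n=50 (the PMM2-CDG minimum). Accrual also refers to a sample size of 100, so n=100 is shown as well.

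**Assumptions.** Two-sided 5% test of a Pearson correlation. The PRO loads a on general severity, its matching finding loads b, and they share nothing else. The documents give neither loading; a=b from 0.3 to 0.7 is shown.

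**Step 1: smallest significant correlation.** r = t/√(n−2+t²). At n=150, t=1.976, so r = 1.976/√(148+3.905) = 0.160, or 2.6% of variance. The values are 0.197 at n=100 and 0.279 at n=50.

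**Step 2: expected matched correlation without domain content.** r = a×b, for example 0.5×0.5 = 0.25.

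**Step 3: chance of significance by Fisher z.** z = atanh(r)×√(n−3), and the chance is Φ(z−1.96)+Φ(−z−1.96). For r=0.25 and n=150: z = 0.2554×12.124 = 3.10, and Φ(1.14) = 0.87.

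| Loading a=b | Expected r | n=150 | n=100 | n=50 |
|---|---|---|---|---|
| 0.3 | 0.09 | 19% | 14% | 9% |
| 0.4 | 0.16 | 50% | 36% | 20% |
| 0.5 | 0.25 | 87% | 71% | 42% |
| 0.6 | 0.36 | 99.5% | 96% | 73% |
| 0.7 | 0.49 | about 100% | about 100% | 96% |

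The plan lists several kinds of matching finding and no rule for combining them. With three comparators at n=150 (4,000 simulated studies), at least one is significant in 47%, 99% and about 100% of studies at loadings 0.3, 0.5 and 0.7. All three are significant in 1%, 69% and about 100%.

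**Step 4: does a matched-minus-non-matched contrast help?** Williams test for dependent correlations, two-sided 5%, n=150, simulated:

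- No domain content, with both subdomains loading equally on general severity: the contrast favours the matched subdomain in 2 to 3% of studies.
- True specific loadings of 0.4, 0.5 and 0.6 on PRO and matched subdomain, general loading 0.6 throughout: about 52%, 91% and 100%. At n=50 with specific loading 0.5, about 45%.
- No domain content, but unequal general loadings (PRO/matched/non-matched): about 40% at 0.7/0.7/0.5, 70% at 0.6/0.7/0.3 and 86% at 0.7/0.7/0.3. In the last case the expected correlations are 0.7×0.7 = 0.49 and 0.7×0.3 = 0.21, a gap caused by severity alone.
- Real domain content, with a non-matched subdomain that follows severity more strongly (PRO general 0.5, specific 0.4; matched general 0.4, specific 0.4; non-matched general 0.7): about 3%. The expected correlations are 0.5×0.4+0.4×0.4 = 0.36 and 0.5×0.7 = 0.35.

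The contrast adds information that the matched correlation lacks. Used alone as a gate, it can err in both directions.

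**The case against.** The plan does not say that a significant matched correlation makes a PRO valid. It states a comparison and no verdict. A reader might infer a p<0.05 rule that nearly every PRO would pass, but the documents contain no such rule; the 5% test above is a device for showing size. This objection stands.

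The matched comparison is also not the whole PRO analysis. The PLS step relates PROs to the clinical scores without restriction to matching ones, so a PRO that follows severity could show up there as diffuse association. Adjustment for confounders might include severity. These steps soften the gap without closing it. PLS has no decision rule, and the confounders are unnamed. PRO change against quality of life is a further association without a criterion, and weighted kappa concerns reliability.

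A reader might also infer that almost any PRO will look valid in this cohort. That needs strong shared loadings, and the documents give none. At 0.3 the figure is 19% for one comparator. The Background notes that some CDG types have only tissue-specific symptoms, and variation in the kind of involvement may weaken a common severity factor. This objection also stands, and it limits the size of the claim.

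Finally, one might expect a difference test to settle the matter by admitting only 2 to 3% of non-specific PROs. That holds only when the two subdomains reflect severity equally. Nor does a cross-sectional contrast show whether a PRO responds to change.

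**Conclusion.** The concern holds in a limited form. The stated validity method for each PRO includes no comparison with non-matching domains and names no result that would count against a PRO. A matched association cannot by itself distinguish domain content from overall severity, whatever threshold is applied to it.

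The size is uncertain. At 150 patients, under the assumed two-sided 5% test and equal loadings, a PRO without domain content would be significant against one matching finding in anything from about 19% to practically 100% of studies as the loading rises from 0.3 to 0.7. The documents do not support a claim that most PROs would be wrongly endorsed. They do support the claim that the plan, as written, lacks the contrast needed to tell. Because the data for that contrast are already to be collected, the plan should be changed before analysis.

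**What to change.** Add a paragraph and a small table to the Data Analysis Plan before any PRO analysis:

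1. For each PRO, list the matching and non-matching NPCRS subdomains and the expected pattern of stronger and weaker correlations.
2. Report each correlation with its 95% CI, and the matched-minus-non-matched difference with its 95% CI, by a dependent-correlation method or a patient-level bootstrap.
3. Report the matched association adjusted for overall severity, for example the NPCRS total without the matching subdomain.
4. Describe a PRO as domain-specific only when this evidence together supports it, not from the matched association alone. Do not use the difference test as a sole pass/fail gate, because it misleads when subdomains differ in how strongly they reflect overall severity.

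The cost is some extra analysis and no new data. Precision will be limited in the PMM2-CDG subgroup if it is near its minimum of 50. Some PROs may end up described only as general-severity measures.
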